2.5.2 Study Drug Exposure

Duration of exposure to study drug (days) is defined as date of last exposure – date of first dose +1.

Date of last exposure is the earliest date of the following date:

- date of last dose + 169 days (e.g., the length of treatment period or dosing interval)
- date of end of study
- date of analysis data cutoff

2.5.3 Prior and Concomitant Medication, Prior and Concomitant Anti-hypertensive medication

The definition of prior and concomitant medications are below:

- Prior medication: Start date of the drug < 1st day of study drug administration
- Concomitant medication: (Start date of the medication \geq 1st day of study drug administration) or (Start date of the drug < 1st day of study drug administration and End date of the medication \geq 1st day of study drug administration)

The ATC codes for antihypertension medication are as below:

- C02 - Antihypertensive

- C03 - Diuretics
- C07 - Beta blocking agents
- C08 - Calcium channel blockers
- C09 - Agents acting on the renin-angiotensin system

2.6 Efficacy Assessment

2.6.1 SBP and DBP

Analysis using censoring and analysis using all collected data will be conducted for ABPM and Office Blood Pressure. Analysis using all collected data will be conducted for HBPM

- Censoring data: ABPM/Office Blood Pressure that assessed while patients are on and within 2 weeks after stopping any escape anti-hypertensive medication will be excluded for analysis.
- All collected data: all collected BP data is included in analysis, regardless of the anti-hypertensive escape medication.

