3. INVESTIGATIONAL PLAN

3.1. Summary of Study Design

This is a single dose, randomized, double-blind, placebo-controlled, parallel-group, Phase 1/2 study to evaluate the safety, tolerability, efficacy, PD, and PK of zilebesiran administered SC in Japanese patients with mild to moderate hypertension. A schematic of the study design is provided in [Figure 1](#).

Before randomization, patients will discontinue prior antihypertensive medication(s) (if taking) for a Washout period of a minimum of 3 weeks. Patients who meet all inclusion criteria and none of the exclusion criteria will be randomized 1:1:1, as described in [Section 3.4](#), to receive a single dose of 300 or 600 mg zilebesiran or placebo.

The planned enrollment for this study is 36 Japanese patients with mild to moderate hypertension. Each treatment arm will include 12 patients.

Eligible patients will be admitted to the site on Day -1, and patients who receive a dose of study drug on Day 1 will remain inpatient at the study site until discharge on Day 2. Patients will return to the clinical study site on an outpatient basis during the 6-month DB Treatment Period for safety, tolerability, efficacy, PD, and PK assessments, as outlined in the Schedule of Assessments ([Table 1](#)).

At Month 3, conventional oral antihypertensives may be added per Investigator judgement for 24-hour mean SBP ≥ 130 mmHg by ABPM. After Month 3, oral antihypertensive medications may also be added per Investigator judgement for persistent elevations in blood pressure (eg, office SBP ≥ 140 mmHg, home blood pressure monitoring [HBPM] SBP > 135 mmHg). [Williams 2018]

All patients will complete Safety/PD Follow-up visits and complete assessments as described in [Table 1](#) at Months 9 and 12.

The estimated duration of study participation, inclusive of screening and safety/PD follow-up, is 14 months.

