Months 3 to 6	
Treat to target blood pressure using a CCB and/or thiazide/thiazide-like diuretic:
 
 At Month 3, a CCB and/or a thiazide/thiazide-like diuretic may be added if the 24-hour mean SBP is ≥ 130 mmHg by ABPM. After Month 3, oral antihypertensive medications may also be added per Investigator judgement for persistent elevations in blood pressure (eg, systolic office blood pressure ≥ 140 mmHg or systolic HBPM >135 mmHg).[Williams 2018]
Safety Follow-up period	Treat to target blood pressure using Investigator's choice of oral antihypertensive(s).

Abbreviations: ABPM=ambulatory blood pressure monitoring; ACE=angiotensin converting enzyme; ARB=angiotensin II-receptor blocker; CCB=calcium channel blocker; DBP=diastolic blood pressure; eCRF=electronic case report form; HBPM=home blood pressure monitoring; RAS=renin-angiotensin system; SBP=systolic blood pressure.

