3.4 Handling of missing data

Imputation for missing data is not considered.

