7.1.2 Summary of ABPM/OBP Censored by Concomitant Anti-Hypertensive Medication

Target population	:	Full Analysis Set
Analysis Items	:	SBP, DBP by ABPM and office blood pressure
Group	:	Placebo, Zilebesiran 300 mg, Zilebesiran 600 mg, Total zilebesiran, Overall Total
Time of analysis	:	Refer to section 2.8.1
Content of analysis	:	
 • Calculate the summary statistics of measurement value, change from baseline for each parameter by groups and analysis time points.

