7.1.5 Treatment Responder in ABPM/OBP by Treatment and Visit

Target population	:	Full Analysis Set
Analysis Items	:	Reduction from baseline of ≥ 5 mmHg and ≥ 10 mmHg in SBP by ABPM/OBP
Group	:	Placebo, Zilebesiran 300 mg, Zilebesiran 600 mg, Total zilebesiran, Overall Total
Time of analysis	:	Refer to section 2.8.1
Content of analysis	:	
 • Count the number of patients for each analysis items by groups.
Definition	:	
 • The denominator of proportions is the target population by groups.

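### The censored Month 6 blood pressure means overstate each arm's fall relative to a no-escape question, and no planned analysis uses the earlier readings that led to escape

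*SAP*

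**What the plan says.** Change from baseline at Months 3 and 6 in 24-hour ABPM and in office blood pressure is a secondary endpoint (Protocol section 2, SAP 1.2). SAP 2.6.1 sets up two versions of the data. In the censored version, "ABPM/Office Blood Pressure that assessed while patients are on and within 2 weeks after stopping any escape anti-hypertensive medication will be excluded for analysis". In the other, "all collected BP data is included in analysis, regardless of the anti-hypertensive escape medication".

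SAP 7.1.1 (all collected) and 7.1.2 (censored) carry the same instruction: "Calculate the summary statistics of measurement value, change from baseline for each parameter by groups and analysis time points". SAP 3.4 adds "Imputation for missing data is not considered". Neither document plans a model for blood pressure, a between-arm difference, or a statement of which question each table answers. Protocol 7.2 describes the analyses as mainly descriptive, without formal testing.

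On escape, Protocol Table 3 (section 5.7.2) says "At Month 3, a CCB and/or a thiazide/thiazide-like diuretic may be added if the 24-hour mean SBP is ≥ 130 mmHg by ABPM". Later in the double-blind period the Investigator may also start such drugs when pressure stays high, with office and home readings as examples. Table 3 also allows earlier treatment in defined circumstances. Inclusion criterion 6 requires a 24-hour mean SBP of at least 130 mmHg at entry.

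SAP 7.1.5, headed "Treatment Responder in ABPM/OBP by Treatment and Visit", counts patients with SBP reductions of at least 5 and at least 10 mmHg. Its denominator is the whole Full Analysis Set arm, and it does not say which version of the data it uses.

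**The concern.** The entry and Month 3 escape cut-offs are the same number. A placebo patient whose ambulatory pressure has not dropped below the entry level qualifies for escape at Month 3, and so does a zilebesiran patient with a weak response. Once escape starts, the Month 6 reading leaves the censored table, so what remains is a complete-case mean of patients selected for lower pressure. The Month 3 reading behind much of that selection is in the database, but no planned analysis uses it.

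The Month 6 figures have a stated use. Protocol 3.3 says blood pressure will be examined to see whether the reduction in Japanese patients falls within the range seen in non-Japanese patients. The benchmarks given there are LS mean reductions versus placebo from Study 002: 14.5 and 14.2 mmHg at Month 6 for 300 and 600 mg. The SAP plans no estimate of that kind.

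**Working it through.** **The plan's own figure.** None is given for blood pressure. The only computed design figure is the power for AGT. With both doses pooled (24 v 12), 0.50 / (0.42 × √(1/12 + 1/24)) = 3.37, and 3.37 − 1.96 = 1.41, giving power of 0.92. This agrees with the stated figure of more than 90% but does not bear on this point.

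**Inputs from the documents.** Entry and Month 3 escape cut-offs of 130 mmHg; 12 patients per arm; placebo-corrected effects averaged over the two doses in Protocol 3.3, (16.7 + 15.7)/2 = 16.2 mmHg at Month 3 and (14.5 + 14.2)/2 = 14.35 mmHg at Month 6.

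**Assumptions, not in the documents** (range tried in brackets). Baseline 24-hour SBP normal with mean 143 and SD 9, truncated at 130; SD of change 11 (8 to 14); Month 3 to Month 6 correlation ρ = 0.6 (0.3 to 0.8); probability p of escape if Month 3 SBP is at least 130, 0.7 (0.2 to 0.9); escape effect −9 mmHg (−5 to −12); placebo change 0 (−5 to +5). In the main check, Month 3 ABPM is the only driver of escape. Simulation used 400,000 patients per arm.

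**Formulas.** Let e3 be a patient's Month 3 deviation from the arm's mean change.
- Error of the censored arm mean = ρ × E[e3 | no escape]. The second factor is negative because high Month 3 values are removed.
- Shift of the all-collected arm mean = escape rate × escape effect.

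**Base case, p = 0.7.** Eligible for escape: 86% placebo, 44% zilebesiran.
- Escape rates: 0.7 × 0.86 = 0.60 and 0.7 × 0.44 = 0.31. Patients left of 12: 4.8 and 8.3.
- Censored error on placebo: 0.6 × (−3.67) = −2.2 mmHg. With ρ = 0.3 it is −1.1 and with ρ = 0.8 it is −2.9. On zilebesiran with ρ = 0.6 it is −2.1.
- All-collected shift: 0.60 × (−9) = −5.4 on placebo and 0.31 × (−9) = −2.8 on zilebesiran. The difference becomes −14.4 + 5.4 − 2.8 = −11.8.

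**Varying the escape probability** (placebo / zilebesiran; mmHg; the no-escape difference is −14.3 to −14.4 throughout):

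| p | Left of 12 | Error of censored arm mean | Censored difference | All-collected difference | Model difference |
|---|---|---|---|---|---|
| 0.2 | 9.9 / 10.9 | −0.3 / −0.5 | −14.5 | −13.6 | −14.4 |
| 0.5 | 6.9 / 9.4 | −1.1 / −1.4 | −14.6 | −12.5 | −14.4 |
| 0.7 | 4.8 / 8.3 | −2.2 / −2.1 | −14.3 | −11.8 | −14.4 |
| 0.9 | 2.7 / 7.2 | −4.9 / −3.1 | −12.6 | −11.0 | −14.3 |

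The model column regresses Month 6 change on baseline and Month 3 change in uncensored patients and predicts for everyone, which is the information an MMRM would use. Over all scenarios the censored arm error ran from −0.1 to −6.6, the censored difference from −11.9 to −15.3, and the all-collected difference from −9.8 to −14.0. The model difference stayed within 0.1 of the no-escape value.

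**Adding a later trigger.** This used a second assumption set: baseline mean 142, SD of change 12, effect −15, escape effect −10. A Month 4–5 reading correlated 0.8 with Month 6 led to escape in 50 to 70% of those at 140 or above. The model using Month 3 alone then left errors of −1.4 to −2.6 on placebo and −0.8 to −1.3 on zilebesiran, with a difference of −13.6 to −14.4 against −15. It still did better than the censored means.

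**At 12 per arm**, for p = 0.5 / 0.7 / 0.9. Under the base assumptions, root mean squared error (RMSE) of the placebo mean was 4.6 / 6.0 / 9.2 censored and 4.2 / 5.2 / 7.9 modelled. Under the second set, RMSE of one dose minus placebo was 6.3 / 7.3 / 9.1 censored and 5.9 / 6.7 / 8.5 modelled, a gain of about 6 to 8%. At p = 0.9, three or fewer placebo patients remained in 64% of simulated trials.

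**The case against.** The strongest reply is that the study is descriptive, has 12 patients per arm, and already discloses much of this: paired censored and all-collected tables and mean plots, spaghetti plots, escape use by arm and visit (SAP 7.1.10), and listings. No between-arm contrast is planned, so dilution affects only a difference that a reader forms. For that difference sampling error dominates. The model's gain is small and cannot be relied on at 90% escape, where one check kept it and another reversed it. The all-collected difference, although shifted, had the smallest RMSE at this sample size. All of this stands. It limits the point to a supportive analysis and is a reason to keep the descriptive tables.

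Four stronger readings are tempting, and the documents do not support them.
- A reader might infer that both planned summaries are biased in a known direction. Error here is measured against a no-escape question that neither document adopts. The all-collected table properly answers a treatment-policy question. Only the direction of the censored arm means is established; the censored difference fell on both sides of the no-escape value.
- A reader might infer that Month 3 ABPM triggers escape. It permits escape at the Investigator's discretion, and office and home readings can also prompt it.
- A reader might infer that a model removes the error almost exactly. That holds only where Month 3 ABPM alone drives escape, as the later-trigger check shows.
- A reader might infer that SAP 7.1.5 counts rescued placebo patients as responders. It does not name its data. On all-collected data, placebo patients with a fall of at least 10 mmHg would rise from about 18% without escape to 30 / 34 / 39% for p = 0.5 / 0.7 / 0.9. On censored data, the full-arm denominator would already make escape users non-responders. The supportable criticism is ambiguity.

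**Conclusion.** The point holds as a limited one. Relative to a no-escape question, the censored Month 6 means overstate each arm's fall, by about 1 to 5 mmHg for escape in 50 to 90% of eligible patients when Month 3 ABPM drives escape, and by more if later readings also act. The direction was the same in every scenario. The size rests on assumed SDs, correlations, escape rates and escape effect, none of which the documents give. Only ABPM was simulated; office blood pressure was not quantified.

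The censored difference between arms has no predictable error. A no-escape difference read from the all-collected table would be too small, by about 2.6 mmHg in the base case. Month 3 ABPM is largely unaffected, because the ABPM-based escape decision follows that reading. The primary safety objective is not touched. This is a cheap improvement to the interpretation of a secondary endpoint.

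**What to change.** 1. Keep SAP 7.1.1 and 7.1.2, and state the question each answers: all-collected as treatment policy; censored as a description of patients not on escape, without presenting its means as the no-escape effect.
2. Add a supportive MMRM of change from baseline with terms for baseline, arm, visit and arm-by-visit, using ABPM at Months 3 and 6 and office blood pressure over the double-blind visits. Exclude escape readings as SAP 2.6.1 defines them, but keep each patient's pre-escape data. Report LS means and dose-minus-placebo differences with 95% confidence intervals and no p-values, which fits the descriptive intent of Protocol 7.2 and gives a figure comparable in form with the Study 002 benchmarks.
3. In SAP 7.1.5, name the data used and state that a patient on escape medication, or within 2 weeks of stopping it, counts as a non-responder.

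The cost is SAP wording and one standard model, with no new visits, data or patients. The downside is that the model assumes missing-at-random given observed blood pressure. That is only approximate where office or home readings prompt escape after Month 3, and the estimates will be imprecise at 12 per arm if escape is very common. The SAP should say so beside the results.

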3.3. Justification for Dose

Zilebesiran will be administered as a single dose of 300 or 600 mg SC in this study. These doses of zilebesiran have been selected for further evaluation in a planned Phase 2 study that will inform the doses selected for the Phase 3 program.

These doses were selected based on data from Study 001 and Study 002 that showed robust and durable reduction in serum AGT at these dose levels. Single and multiple doses of zilebesiran up to 800 mg in Study 001 and up to 600 mg in Study 002 were found to have acceptable safety profiles and lead to clinically meaningful reductions in 24-hour mean SBP by ABPM.

- In Study 001 Part A, single ascending doses of zilebesiran from 10 to 800 mg showed dose-dependent reductions in serum AGT and 24-hour mean SBP assessed by ABPM. Zilebesiran also demonstrated an acceptable safety profile at all dose levels. Based on Study 001 results, zilebesiran dose regimens of 150 mg q6M, 300 mg q6M, 600 mg q6M, and 300 mg q3M zilebesiran were selected to be evaluated in Study 002.
- In Study 002, a single dose of 300 or 600 mg zilebesiran (q6M regimens) showed clinically and statistically significant reductions in 24-hour mean SBP by ABPM compared to placebo at Month 3 (LS mean reductions of 16.7 mmHg for 300 mg and 15.7 mmHg for 600 mg) that were sustained through Month 6 (LS mean reductions of 14.5 mmHg for 300 mg and 14.2 mmHg for 600 mg). A dose-dependent reduction from baseline in serum AGT over time was observed across all the zilebesiran dose levels.
- For the proposed dose levels in this study, median reductions in serum AGT were 98.1% and 98.8% at Month 3 and 96.1% and 97.8% at Month 6 for the zilebesiran 300 and 600 mg doses, respectively. A log-linear relationship between reductions in serum AGT and change from baseline in 24-hour mean SBP by ABPM was observed in Study 002 leveraging data from all doses. Both regimens had acceptable safety profiles.

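### Month 6 blood pressure means that leave out readings on escape medication describe selected patients, so within the zilebesiran arms they overstate the reduction and can hide waning since Month 3.

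*SAP*

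**What the plan says.** Two versions of the ABPM and office blood pressure summaries are planned (SAP 2.6.1). In the censored version, readings "assessed while patients are on and within 2 weeks after stopping any escape anti-hypertensive medication will be excluded for analysis". In the other, "all collected BP data is included in analysis, regardless of the anti-hypertensive escape medication". For the censored table (SAP 7.1.2) the instruction is "Calculate the summary statistics of measurement value, change from baseline for each parameter by groups and analysis time points", and SAP 7.1.9 plots the corresponding means with standard errors. There is no model, and SAP 3.4 states "Imputation for missing data is not considered".

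The escape rules are in the protocol. Section 3.1: "At Month 3, conventional oral antihypertensives may be added per Investigator judgement for 24-hour mean SBP ≥ 130 mmHg by ABPM". Later, "oral antihypertensive medications may also be added per Investigator judgement for persistent elevations in blood pressure". Table 3 in Section 5.7.2 repeats the Month 3 rule: "At Month 3, a CCB and/or a thiazide/thiazide-like diuretic may be added if the 24-hour mean SBP is" at or above 130 mmHg. Inclusion criterion 6 (Section 4.1) uses the same 130 mmHg threshold for entry.

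Change in ABPM and office pressure at Month 3 and Month 6 is a secondary endpoint (Protocol 2, SAP 1.2). Protocol 3.3 also intends to judge whether the reduction in Japanese patients lies within the range seen in non-Japanese patients. The Month 6 benchmark given there, from Study 002 and relative to placebo, is "LS mean reductions of 14.5 mmHg for 300 mg and 14.2 mmHg for 600 mg".

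**The concern.** Whether a patient has a Month 6 value in the censored table depends on that patient's own blood pressure at Month 3 or later. In a zilebesiran arm the patients removed are mainly those whose pressure fell least. The rest are a favourable selection, and their plain mean is not the arm's mean. The figure in SAP 7.1.9 then joins a Month 3 mean over nearly everyone to a Month 6 mean over the selected patients, so a real loss of effect can look like a plateau or a gain.

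The all-collected version keeps everyone but adds the effect of the escape drugs to the Month 6 values. Neither version estimates what Month 6 pressure would have been without escape medication, and that is what a reader needs to judge whether a single dose lasts six months or to set the result beside Study 002.

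**Working it through.** **Plan's own figures.** The documents give no expected escape uptake, no blood pressure SD and no expected number left after censoring. The one design figure, power above 90%, concerns serum AGT and does not bear on this point.

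**Inputs from the documents.** 12 patients per arm; entry and Month 3 escape threshold both 130 mmHg; Study 002 placebo-corrected 24-hour SBP effects of 16.7 and 15.7 mmHg (Month 3) and 14.5 and 14.2 mmHg (Month 6) for 300 and 600 mg. Averages: (16.7 + 15.7)/2 = 16.2 and (14.5 + 14.2)/2 = 14.35, so true waning is 16.2 − 14.35 = 1.85 mmHg.

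**Assumed, not in the documents.**
- Model A: usual SBP normal with mean 140 and SD 9; visit SD 6; entry reading at least 130; patient-to-patient SD of effect 7; 75% of those at or above 130 at Month 3 receive escape; escape lowers SBP by 10. Varied: mean 137–144, uptake 50–90%.
- Model B: baseline mean 138–146, SD 10, cut at 130; SD of change 9–12; Month 3–Month 6 correlation 0.5–0.7; placebo change 0 (also −5 and +5); uptake 50, 80 or 100%; escape lowers SBP by 8.

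Both simulate 24-hour SBP with the Month 3 trigger only. Office pressure, DBP and later triggers follow the same logic but were not sized.

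**Identity.** With a share p of patients uncensored, true mean = p × (mean of uncensored) + (1 − p) × (escape-free mean of escaped). The all-collected mean equals the true mean plus (1 − p) × (escape effect).

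**Within the zilebesiran arm, Model A, central case.** Uncensored 8.7 of 12, so p = 0.725. Mean change: −17.2 at Month 3; −15.4 at Month 6 without escape; −17.3 censored.
- Overstatement: 17.3 − 15.4 = 1.9 mmHg. The censored Month 6 mean matches Month 3, so the waning vanishes.
- Implied escape-free mean of the escaped patients: (−15.4 + 0.725 × 17.3)/0.275 ≈ −10.4. The patients dropped are the weak responders.
- All collected: −15.4 − 0.275 × 10 ≈ −18.2, an overstatement of 2.8 mmHg.

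Over the Model A range the censored overstatement is about 1.0 to 2.8 mmHg. In Model B it is present in every setting, from about 0.7 to 5.5 mmHg. In Model B's central case (baseline mean 142, SD of change 12, correlation 0.6) at 80% uptake, the 300 mg arm reads −16.7 at Month 3 and −17.3 at Month 6 censored, when the truth is −14.5.

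**Patients left at Month 6, of 12 per arm.**

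| Uptake | Placebo | Each zilebesiran arm |
|---|---|---|
| 50% (B) | 6.5–7.2 | 8.9–10.0 |
| 75% (A, central) | 3.9 | 8.7 |
| 80% (B) | 3.2–4.4 | 7.0–8.7 |
| 100% (B) | 1.0–2.5 | 5.7–7.9 |

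The placebo ranges are for a placebo change of 0. In Model B's central case the chance that three or fewer placebo patients remain is 2%, 40% and 88% at 50, 80 and 100% uptake.

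**Contrast with placebo at Month 6 (truth about −14.4).**

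| | Censored | All collected |
|---|---|---|
| Model A, central | −15.6 | −10.4 |
| Model A, range | −15.0 to −16.3 | −9.4 to −12.0 |
| Model B, range | −8.4 to −15.0 | −10.4 to −13.0 |

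The all-collected contrast is diluted throughout, because more placebo patients receive escape. In Model A, placebo p = 3.9/12 = 0.325, so its shift is −0.675 × 10 = −6.75 against −2.75 in zilebesiran, and −14.35 − 2.75 + 6.75 = −10.35. The censored contrast goes either way, because placebo is selected too.

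**Does a model recover the truth?** Predicting the censored Month 6 values from baseline and Month 3 pressure, fitted to uncensored patients, gave contrasts of −14.3 to −14.4 in Model A. In Model B's central case it gave −14.5 (300 mg), −14.2 (600 mg) and 0.0 to +0.2 (placebo). These are large-sample checks in which escape depends only on observed Month 3 pressure.

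**Simple alternatives.** Carrying the Month 3 value forward looks adequate when waning is mild. With a true Month 6 effect of −8.0 in Model A it gives a contrast of −10.0, worse than plain censoring at −9.3. Showing the Month 3 mean of the same uncensored patients exaggerates waning: −20.3 to −17.3 is a 3.0 mmHg loss when the truth is 1.85.

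**The case against.** The plan is open about the censoring. The all-collected version is tabulated and plotted (SAP 7.1.1, 7.1.7, 7.1.8), the number of patients is part of every summary (SAP 4.1.1), escape use is reported by arm (SAP 7.1.10), and the title of 7.1.2 names the censoring. The analysis is descriptive with no formal testing (Protocol 7.2), the primary objective is safety, and the censored version is not named as the main one. Month 6 durability is also informed by serum AGT, which is not censored for escape, and by Study 002. A shift of 1–3 mmHg is smaller than the noise: with 12 per arm, the trial-to-trial SD of the censored difference is about 5.8 mmHg in Model A.

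All of that stands and limits the severity. It does not remove the defect: a reader can see how many patients were removed but cannot recover the unselected mean, and in a descriptive study the description is the result.

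Two stronger readings are tempting. One is that the plan overstates zilebesiran's effect against placebo. The documents do not support this: placebo is selected as well, the censored contrast may be too large or too small, and the all-collected contrast is too small. The other is that censoring will remove most of the placebo arm. Escape is at the investigator's discretion and no uptake is stated; at 50% about 6 to 7 of 12 remain.

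**Conclusion.** The concern holds for the within-arm means. The rule removes Month 6 readings because of earlier high pressure, and under both sets of assumptions the censored zilebesiran mean is too favourable: by about 1–3 mmHg at 50–90% uptake in Model A and 0.7–5.5 mmHg in Model B. That is enough to mask the waning of about 1.9 mmHg seen in Study 002. The all-collected mean errs the same way within the arm and understates the contrast with placebo.

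The censored contrast with placebo is best called unreliable, without a stated direction. Few placebo patients may remain if uptake is high (about 4 of 12 at 75%), but this is a risk and not a consequence of the plan. The direction of the within-arm error follows from the rule and held in every setting run; its size rests on assumed SDs, uptake and escape effect. For a descriptive secondary endpoint this is a should-fix.

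**What to change.** In SAP 7.1.2 and 7.1.9:

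1. State the target as blood pressure had no escape medication been given.
2. Add a repeated-measures model on the uncensored readings with arm, visit, arm-by-visit and baseline pressure, taking Month 3 and the other pre-escape visits as outcomes. Report Month 3 and Month 6 estimates with confidence intervals, per arm and versus placebo. The model imputes nothing, so SAP 3.4 can stand, and intervals without tests fit the descriptive aim. Specify the covariance structure in advance: ABPM has only two post-baseline visits, but office pressure has ten up to Month 6 (Days 2, 3, 8 and 15, Months 1 to 6), which is many for 36 patients.
3. Retitle the present censored table *patients not on escape medication*, and show the number observed and the number escaped, per arm and visit, beside each mean and on the figures.
4. Use carry-forward of the last pre-escape reading at most as a labelled sensitivity analysis, with a note that it assumes no waning in escaped patients.

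The cost is SAP text, one table and one figure, with no new data or patients. The model assumes that escape depends on observed pressure. This is only approximate where the trigger was a home reading, or an ABPM reading when office pressure is being modelled. Placebo estimates will be imprecise if few patients stay uncensored.
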